##### Cognitive Function

Neuropsychological tests will be administered in a quiet laboratory testing room on a Dell® desktop computer running on Windows XP® at the CIRNA. Unless otherwise noted, all tasks will be administered via E-Prime 2.0 (Psychology Software Tools, Inc.). The computerized battery is administered in a random order using clickable icons. Total administration time is ~ 30 minutes. The tasks are:

- Visual/Spatial-N-Back: 3-back version (VSNB3). The n-back is one of the most commonly used paradigms in neuroimaging studies investigating the neurological underpinnings associated with maintenance and retrieval of information in working memory (Owen, McMillan, Laird, & Bullmore, 2005). The current study employs a visuo-spatial working memory task that is based on the visuo-spatial n-back paradigms used in prior research (Ehlis, Bahne, Jacob, Herrmann, & Fallgatter, 2008; Green et al., 2005; Owen, et al., 2005). During the n-back, participants are instructed to remember the location of a stimulus, a grey circle that is approximately 5 cm in diameter, as it appears randomly in 8 possible locations around the perimeter of a computer screen. The stimulus will appear for 200 ms, followed by an interstimulus interval (ISI) of 2800 ms. A cross hair will remain visible during the stimulus presentation to cue participants to look at the center of the screen so that all stimuli appearing around the perimeter of the screen can be seen clearly. The n-back task includes 4 conditions of varying difficulty levels: the 0-back, 1-back, 2-back, and 3-back. Participants respond only to targets (30% of stimuli) by pressing the SPACEBAR. They are instructed to do nothing on other trials.

Each of the task conditions (0-, 1-, 2- & 3-back) will be administered in a pseudorandomized counterbalanced order. Each difficulty level will consist of 1 block of 50 trials, preceded by a practice block

of 20 trials. During the 0-back, participants are instructed to press the SPACEBAR if the stimulus appears in a predetermined location (designated as the upper left corner of the computer screen). The 0-back serves as a baseline condition of the n-back, during which participants are engaged in a task that does not require storage or manipulation of information in working memory, but is otherwise analogous to the other n-back conditions. During the 1-back, participants are instructed to press the SPACEBAR whenever the stimulus appears in the same location as the stimulus that immediately preceded it and to do nothing if the stimulus appears in any other location. During the 2- and 3-back conditions, participants are instructed to press the SPACEBAR whenever the stimulus appears in the same location as the stimulus that preceded it by 2 or 3 trials, respectively. The primary dependent variables for this task are total number of correct responses and reaction time. Time: approximately 16 min.

- Penn Continuous Performance Test - Number/Letter Version (PCPT-nl). The PCPT-nl is a measure of visual attention and vigilance based on the Penn CPT (Kurtz et al., 2001). In this task, a series of red vertical and horizontal lines (7-segment displays) flash in a digital numeric frame (resembling a digital clock). The participant must press the spacebar whenever these lines form complete numbers or complete letters. The task is divided in two parts, each lasting three minutes: in the first part the participant is requested to respond to numbers and in the second part the response is to letters. The participant practices both sets of trials before the task begins. Time: approximately 10 min with practice.

For both measures, median reaction time for correct responses measures cognitive performance. These tasks will be administered at Pre-Quit, Target Quit Day, and Weeks 3 and 12.

#### Withdrawal Symptoms and Cravings

Minnesota Nicotine Withdrawal Scale (MNWS-W) (with a one-week frame of reference) will measure withdrawal symptoms associated with quitting smoking. The Likert-style scale assesses 7 DSM-IV items of nicotine withdrawal (e.g., restlessness, irritability).

Craving will be assessed by the well-validated Questionnaire of Smoking Urges (QSU-B). The QSU contains 10 items forming 2 subscales (anticipation of reward, relief from negative affect) with established reliability. Cravings to smoke following a quit attempt have been related to cessation.

These measures will be administered at Pre-Quit, Target Quit Day, and Weeks 3, 7, and 12.

#### Treatment Measures.

##### Varenicline Adherence

Varenicline adherence will be assessed by self-report using a time-line follow-back procedure and by pill count and the collection of used blister packs at each visit during the treatment period as done in past varenicline trials (e.g., Gonzales et al., 2006; Jorenby et al., 2006; Ebbert et al., 2009). We will also collect blood samples (10 mL) at Weeks 3 and 12 to assess varenicline levels as an additional measure of adherence and to examine the validity of self-report and pill count data. An adherence covariate will represent the proportion of total dose taken. These biosamples will be shipped to the laboratory of [name] at the University of California San Francisco for analysis. These blood samples will not be collected if the participant has not taken the study medication for 14+ days.

##### Side Effects

As in our past varenicline trials (Patterson et al., 2009; [name] et al., 2011), a checklist and open-ended questions will assess the frequency and severity of varenicline-related side effects at all time-points after the Intake Session over the course of the 24-week study, before and after medication initiation. These assessments monitor participant safety and dose reductions or suspension can occur. Side effects will be a study outcome and can be a covariate in the analysis as the overall frequency and/or as the presence (ever) of specific side effects. This measure includes psychiatric events (e.g., depressed mood, suicidal ideation; Kuehn, 2008) and cardiovascular side effects.

## **Outcomes Variables.**

### **Abstinence (primary)**

Smoking status will be assessed using the timeline follow-back method (Brown et al., 1998) as done previously (Lerman et al., 2004; [name] et al., 2010b) and by using urinary cotinine to biochemically verify the self-report. Participants will be considered to be abstinent if they self-report abstinence (not even a puff of a cigarette) for >7 days prior to the assessment at Weeks 12 and 24 and have a urine cotinine <100ng/ml at the time-point (SRNT, 2002; Hughes et al., 2003). As per convention, participants are assumed to be smoking if they self-report to be smoking at the time-point, cannot be reached to provide data at the time-point, fail to provide a urine sample at the time-point, or provide a urine sample at the time-point that is >100ng/ml (SRNT, 2002).

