### **Outcome Assessments.**

The primary outcome variable for Aims 1 and 3 is 7-day point prevalence abstinence at Weeks 12 and 24, biochemically-confirmed with urine cotinine (Hughes et al., 2003). Secondary outcomes for Aim 1 include: biochemically-confirmed 7-day point prevalence abstinence at Week 18, smoking rate at Weeks 12, 18, and 24 for non-abstainers, prolonged abstinence to Weeks 12, 18, and 24, continuous abstinence at Weeks 12, 18, and 24, time to 7-day relapse (no grace period), and lapse and recovery events. For Aim 2, since individuals with HIV/AIDS who smoke report a lower QOL (Webb et al., 2007), we will closely monitor QOL, as measured by a commonly-used self-report scale for this population, and administer a checklist of varenicline-related side-effects.

Based on enrollment date, subjects will complete social impact assessments as part of a sub-study in collaboration with the Treatment Research Institute. Two assessments administered at Weeks 3, 7, and 12, include the self-administered, computer based ACASI-SHQ and the staff administered HVTN Social Impact Assessment. An additional client evaluation form is completed by participants at Week 12. Participants who miss administration sessions may complete the assessments at their subsequent study session.

Participants who are unable to quit smoking may be given referrals for smoking cessation treatment following the Week 24 assessment.

**Note:** If a participant is unable to complete a session in-person, assessments and counseling may be completed over the telephone. Participants will receive compensation for their time at the following in-person session.

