**Table 2: Study Measures/Events**

Study Week	-1	0	1	3	5	7	9	12	18	24
Session Name	Intake	Pre-Quit	TQD	W3	W5	W7	W9	W12	W18	W24
TREATMENT										
Varenicline/Placebo		X	X	X	X	X	X	X	X	
Counseling		X	X	X	X	X	X			
SCREENING/COVARIATES										
Urine Pregnancy Screen	X									
Breath Alcohol Concentration	X									
Blood Pressure	X	X	X	X	X	X	X	X	X	X
Depression/Anxiety (HADS)	X	X	X	X	X	X	X	X	X	X
Demographics	X									
Smoking History/FTND	X									
ETOH History	X									
Medical History	X									
Psychiatric History (MINI)	X		X g							
Adherence to Antiretrovirals Instrument		X			X		X	X	X	X
Pharmacy Refill Data		X d			X d			X c		X c
Concomitant Medications	X	X	X	X	X	X	X	X	X	X
Creatinine Clearance	X a									
Viral Load Assessment								X e		
Nicotine Metabolite Ratio	X									
Genetic Polymorphisms	X									
Bipolar Disorder Symptoms (MADRS f , YMRS, Additional Screener, MINI) g	X		X	X	X	X	X	X	X	X
MEDIATING VARIABLES										
Affect (PANAS)		X	X	X		X		X		
Cognitive Function (N-back, CPT)		X	X	X				X		
Nicotine Withdrawal (MNWS-W)		X	X	X		X		X		
Smoking Urges (QSU-B)		X	X	X		X		X		
TREATMENT VARIABLES										
Adherence (Pill Count)			X	X	X	X	X	X		
Adherence (Blood)				X i				X i		
Side Effects Checklist (SEC)		X	X	X	X	X	X	X	X	X
Side Effects (Open-Ended)			X	X	X	X	X	X	X	X
Suicidality (C-SSRS)	X	X	X	X	X	X	X	X	X	X
OUTCOMES										
Carbon Monoxide (CO) Test	X	X	X	X	X	X	X	X	X	X
Smoking Rate (TLFB)		X	X	X	X	X	X	X	X	X
Urine Cotinine								X b	X b	X b
Quality of Life (HAT-QoL)		X	X	X	X	X	X	X	X	X
ACASI-SHQ h				X		X		X		
HVTN Social Impact Assessment h				X		X		X		
Client Evaluation Form h								X		

\*TQD = Target Quit Day

\*W= Week

\*Note: Target Quit Day visit may occur +3 days from target date; Week 3, 5, 7, 9, 12, 18, and 24 visits may occur +/- 1 week from target date.

a Will only be completed on initially eligible participants who have not had this test within last 6 months.

b Will only be completed on participants who self-report abstinence for  $\geq$  7 days prior to the assessment.

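### The primary abstinence rule asks for more than 7 smoke-free days, but the endpoint's name and the urine-testing rule use 7, so a participant with exactly 7 days has no defined outcome

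*Combined protocol and SAP*

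**What the plan says.** Four places in the combined protocol and SAP bear on the primary outcome.

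- **Name of the outcome.** Outcome Assessments states: "The primary outcome variable for Aims 1 and 3 is 7-day point prevalence abstinence at Weeks 12 and 24", confirmed by urine cotinine. The abstract, Aim 1 under Overall Objectives, and the Aim 1 power paragraph also name a 7-day outcome.
- **Who is tested.** Table 2 schedules urine cotinine at Weeks 12, 18 and 24. Footnote b limits it to "participants who self-report abstinence for $\geq$ 7 days prior to the assessment".
- **Who is abstinent.** Abstinence (primary) requires that participants "self-report abstinence (not even a puff of a cigarette) for >7 days prior to the assessment at Weeks 12 and 24" and have cotinine below 100 ng/ml.
- **Who is smoking.** In the same section, "participants are assumed to be smoking if they self-report to be smoking at the time-point", if they cannot be reached, if they "fail to provide a urine sample at the time-point", or if the sample is above the cut-off.

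On telephone visits, the note closing Outcome Assessments says: "If a participant is unable to complete a session in-person, assessments and counseling may be completed over the telephone". It makes no exception for Weeks 12 and 24, and adds: "Participants will receive compensation for their time at the following in-person session". The note to Table 2 lets the Week 12, 18 and 24 visits fall up to one week either side of the target date.

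**The concern.** A binary primary endpoint needs a rule that gives every randomised participant one value. Here the abstinence definition and the smoking list are written separately and do not meet at the boundary. The abstinence definition is also stricter than the endpoint's name and than the rule that decides who is tested.

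A programmer who codes from the abstinence definition, with everyone else a smoker, would score a 7-day participant as smoking. One who codes from the smoking list, with everyone else abstinent, would score the same person as abstinent. That choice belongs in the plan and should be settled before outcomes are seen by arm.

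The telephone note raises a smaller matter of the same kind. A participant who reports abstinence by telephone at a primary time-point needs a urine sample to be counted, and the plan does not say how or when it is collected.

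**Working it through.** The plan states no figure that depends on this rule, so the check is a comparison of the passages.

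**Step 1: unit of measurement.** Smoking is recorded by timeline follow-back as daily smoking (Other Smoking Measures). In whole days, more than 7 means 8 or more, and at least 7 means 7 or more.

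**Step 2: apply each rule at an in-person Week 12 or Week 24 visit.** Other Smoking Measures treats NicAlert levels 3-6 as smoking and levels 0-2 as non-use.

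| Smoke-free days reported | Urine taken (footnote b) | Dipstick level | Meets abstinence definition | Meets a smoking condition |
|---|---|---|---|---|
| 6 or fewer | No | none | No | Yes |
| Exactly 7 | Yes | 0-2 | **No** (7 is not more than 7) | **No** |
| Exactly 7 | Yes | 3-6 | No | Yes |
| 8 or more | Yes | 0-2 | Yes | No |
| 8 or more | Yes | 3-6 | No | Yes |

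Only the second row has no outcome. That participant was reached, gave a sample, reported no smoking in the 7-day window, and had a negative result.

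**Step 3: size.** The documents do not say how many participants would report exactly 7 days. To fall in the gap, the last smoking day must be one particular calendar day before the visit, so the group should be narrow. For illustration only, assume that a share *f* of 1% to 4% of those meeting the 7-day rule have exactly 7 days, equally in both arms, and that all are coded as smoking. The change is then *f* × rate, using the expected rates in the Aim 1 power paragraph:

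| | Expected rate or difference | × 0.01 | × 0.04 |
|---|---|---|---|
| Week 12 placebo | 21.2% | 0.21 points | 0.85 points |
| Week 12 varenicline | 50.3% | 0.50 | 2.01 |
| Week 12 difference | 50.3 − 21.2 = 29.1 points | 0.29 | 1.16 |
| Week 24 placebo | 14.5% | 0.15 | 0.58 |
| Week 24 varenicline | 33.5% | 0.34 | 1.34 |
| Week 24 difference | 33.5 − 14.5 = 19.0 points | 0.19 | 0.76 |

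If the same people are coded as abstinent, the change is zero. The written rules do not decide between the two.

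**Step 4: telephone visits.** The telephone note permits remote assessment but does not waive urine. The smoking list refers to a sample at the time-point, not at the session, and the visit window is one week either side. A sample given in person within the window is therefore compatible with the text. No section provides for it, however, and Table 3 lists no session after Week 24 at which the deferred payment could be made.

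**The case against.** **The symbol may be an extraction artefact.** A greater-or-equal sign drawn as an underlined character could have been read as a plain greater-than sign. This cannot be excluded without the source PDF. Against it, the extracted text keeps the at-least sign elsewhere, including footnote b. If the source shows at least 7, the main point falls away.

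**Everything else says 7 days, so no one would apply 8.** This is likely in practice. It shows which reading was intended, but the operative definition still says something different.

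**The telephone rule is a disclosed convention.** Most of this stands. Coding missing outcomes as smoking is stated openly. The Missing Data paragraph concedes that it can narrow the difference between arms, adds a completers-only analysis, and examines whether missing outcomes relate to treatment arm. A manual of operations is also planned and could hold the collection step. What remains is a missing instruction.

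**Stronger readings that the documents do not support:**

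- A reader might infer that telephone reporters are true abstainers wrongly counted as smokers. The endpoint is biochemically confirmed, so without a sample their abstinence is not established.
- A reader might infer a loss of power. The plan gives no share of telephone visits, and it presents its planning rates as already cotinine-confirmed, so there is no basis for discounting them again.
- A reader might see the same gap at exactly 100 ng/ml, which is neither below nor above the cut-off. The assay is a dipstick with seven levels, and every level is classified, so the case does not arise.

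**Conclusion.** As written, the primary abstinence definition conflicts with the endpoint's name and with footnote b. It leaves a participant with exactly 7 smoke-free days and a negative dipstick without an outcome. This rests on the extracted symbol being correct and on days being counted whole.

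It would go too far to say that the rule lowers the measured quit rates. These participants are unclassified, not expressly coded as smoking, so no direction follows from the text. The effect is probably small and its size is not in the documents; the 1% to 4% range above is an assumption.

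The telephone gap is secondary and operational. Severity overall: minor, but worth correcting because it concerns the primary endpoint.

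**What to change.** 1. Check the symbol in the source PDF. If it is a plain greater-than sign, change the self-report criterion in Abstinence (primary) to at least 7 days, matching Table 2 footnote b. No change to the cotinine wording is needed.
2. Add one sentence to the telephone note in Outcome Assessments. A telephone report of at least 7 days' abstinence at Week 12 or 24 is followed by urine collection within the existing window of one week either side. The 7-day question is repeated at collection so that report and sample refer to the same date, and the session and travel payments are made then. A participant who gives no sample is still coded as smoking. The same sentence can cover Week 18.

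The first change costs one edit. The second costs a sentence and a few collection visits, using the $20 travel payment already in Table 3. Its one drawback is that the sample may come some days after the call, which repeating the question addresses.

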### **Other Smoking Measures (secondary)**

As per recommendations (Hughes et al., 2003), secondary smoking outcomes include: prolonged abstinence to Weeks 12 and 24 (relapse is 7 consecutive days of self-reported smoking, after a 2-week grace period), continuous abstinence at Weeks 12 and 24 (no smoking between the quit day and the follow-up; no smoking during weeks 9-12 as measured in previous varenicline trials with the general population of smokers; Gonzales et al., 2006), time to 7-day relapse (no grace period), smoking rate, and lapse (smoking episodes not lasting 7 days) and recovery (return to 24-hour abstinence) events (see [name] et al., 2010b). Abstinence and smoking rate outcome will also be available for Week 18.

**Cessation/Smoking Rate:** Daily smoking (presence and rate) will be assessed at each visit after Intake Session with the well validated timeline followback method (TLFB). These data can be used to assess the timing and rates of lapses (smoking episodes not lasting 7 days), recovery events (return to abstinence), and relapse events, as well as to monitor changes in smoking rates (i.e., # cigarettes/day). These data will also be used to compute and assess secondary measures of smoking cessation (e.g., continuous and prolonged abstinence).

**Carbon Monoxide (CO) Test:** Carbon monoxide will be measured at Intake and all subsequent visits to confirm smoking status.

**NicAlert™ Urine Dipstick (cotinine assessment):** Smoking status will be assessed with NicAlert™ urine dipsticks from Nymox Pharmaceutical Corporation

([http://www.nymox.com/products/nicalert/product\\_insert\\_for\\_urine.html](http://www.nymox.com/products/nicalert/product_insert_for_urine.html)). A midstream urine sample of approximately 25mL will be used to test for the presence of cotinine. Results will appear in one of seven category levels of usage. Level 0 indicates no detectable tobacco use; levels 1-2 indicate presence of cotinine, but as a non-user, and levels 3-6 indicate cotinine consistent with tobacco use. Participants with results in levels 3-6 will be considered smokers. The NicAlert™ urine cotinine assessment will be used to verify smoking status at Weeks 12, 18, and 24.

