abstinence at weeks 12 and 24. Secondary outcomes include: prolonged abstinence to week 12, 18, and 24 (relapse defined as 7 consecutive days of self-reported smoking, after a 2-week grace period), continuous abstinence at weeks 12 and 24 (e.g., no smoking between quit day and follow-up), time to 7-day relapse (no grace period), and lapse and recovery events. The trial results may support the use of varenicline for the treatment of nicotine dependence among those with HIV/AIDS, thereby reducing tobacco-related morbidity and mortality in this population.

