## CHARACTERISTICS OF THE STUDY POPULATION

### 1. Target Population

Three hundred ten adult male and female smokers 18 years of age or older who have been diagnosed with HIV/AIDS (identified through the UPENN CFAR Clinical Core, UPHS PennChart reviews and community-based HIV/AIDS organizations and events) and smoke at least 5 cigarettes per day will complete the study.

At PENN, a previous nicotine patch trial recruited a sample comprised of 45% women and 16% racial/ethnic minorities ([name] et al., 2010b). A separate PENN smoking cessation trial that used targeted efforts to recruit minority smokers had a sample comprised of 55% women and 52% racial/ethnic minorities ([name] et al., 2011). The UPENN CFAR Clinical Core population is 78% African American and 4% Hispanic American.

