### 3. Key Inclusion Criteria

Eligible subjects will be males and females:

1. 18 years of age or older who self-report smoking at least 1 cigarette (menthol and non-menthol) per day, on average.
2. Diagnosed with HIV infection and exhibiting viral load of  $\leq 1000$  copies/mL within the last 6 months.
3. Exhibiting CD4+ count of  $\geq 200$  cells/mm^3 within the last 6 months.
  1. If the participant has not had a CD4+ count test completed in the last 6 months, an older result ( $\geq 200$  cells/mm^3) may be used if evidence is provided that all subsequent viral loads results are  $\leq 1000$  copies/mL.
4. Able to use varenicline safely, based on a medical evaluation including medical history and psychiatric evaluation.
5. Residing in the geographic area for at least 7 months.
6. Women of childbearing potential (based on medical history) must consent to use a medically accepted method of birth control (e.g., condoms and spermicide, oral contraceptive, Depo-Provera injection, contraceptive patch, tubal ligation) or abstain from sexual intercourse during the time they are taking study medication and for at least one month after the medication period ends.
7. If current or past diagnosis of bipolar disorder (I, II, or NOS), eligible if:
  - a. No psychotic features
  - b. MADRS: total score  $\leq 8$  (past 4 weeks), suicidal item score  $\leq 1$  (past 4 weeks)
  - c. Y-MRS: total score  $\leq 8$  (past 4 weeks), irritability, speech content, disruptive, or aggressive behavior items score  $\leq 3$  (past 4 weeks)
  - d. No psychiatric hospitalization or Emergency Room visits for psychiatric issues in the past 6 months

- e. No aggressive or violent acts or behavior in the past 6 months
- 8. Able to communicate fluently in English.
- 9. Capable of giving written informed consent, which includes compliance with the requirements and restrictions listed in the combined consent/HIPAA form.

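### Prolonged abstinence and time to relapse fail only on seven consecutive self-reported smoking days, so recurrent intermittent smoking and a failed cotinine test can both be scored as abstinence

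*Combined protocol and SAP*

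**What the plan says.** The Protocol Abstract lists prolonged abstinence to Weeks 12, 18 and 24 with "relapse defined as 7 consecutive days of self-reported smoking, after a 2-week grace period". Other Smoking Measures (secondary) repeats the rule ("relapse is 7 consecutive days of self-reported smoking, after a 2-week grace period") and lists time to 7-day relapse without a grace period. Shorter runs are classed separately, as "lapse (smoking episodes not lasting 7 days) and recovery (return to 24-hour abstinence) events". One smoke-free day therefore closes an episode and restarts the count.

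The data source is the daily timeline follow-back (TLFB): "These data will also be used to compute and assess secondary measures of smoking cessation (e.g., continuous and prolonged abstinence". No cotinine or carbon monoxide requirement is attached to these outcomes. Abstinence (primary) is stricter. It requires no puff for the 7-day window and urine cotinine below 100 ng/ml, and it counts a missing contact, a missing sample or a result above 100 ng/ml as smoking. Table 2, footnote b, limits urine cotinine to participants who self-report at least 7 days of abstinence. Carbon monoxide is measured at every visit, but with no cut-off and no stated link to prolonged abstinence.

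On entry, Key Inclusion Criteria admit adults "who self-report smoking at least 1 cigarette (menthol and non-menthol) per day, on average", while Target Population describes participants who "smoke at least 5 cigarettes per day will complete the study".

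Data Analysis, Aim 1, treats prolonged and continuous abstinence as further measures of quit rates, analysed by logistic regression like the primary.

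**The concern.** There are two separate gaps.

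First, a rule that fails only on an unbroken seven-day run does not recognise a return to regular but non-daily smoking. Such a participant is counted among the prolonged abstainers and contributes no event to time to relapse, however long the pattern lasts.

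Second, because the rule rests on self-report alone, one visit can yield contradictory classifications. A participant who denies smoking and fails the cotinine test is a smoker on the primary outcome, but stays abstinent on the prolonged and continuous measures.

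What is at stake is the meaning of the supporting analyses for Aim 1. They are to be reported as quit rates, but they would include people who have not quit.

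**Working it through.** The documents give no rate or power figure for prolonged abstinence, so there is nothing to reproduce. The check applies the rule as written to daily smoking calendars.

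**Inputs.** The relapse event is a run of at least 7 smoking days (Other Smoking Measures). Quit day is Week 1 (Behavioral Counseling). The start of the grace period is not stated; I assume it runs from quit day and so ends at Week 3. The windows are then:
- Week 3 to 12: 9 × 7 = 63 days
- Week 3 to 24: 21 × 7 = 147 days
- Week 1 to 24, no grace period: 23 × 7 = 161 days

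**Best-spaced extreme.** With one smoke-free day on the same weekday every week, smoking days are 6/7 × 63 = 54, 6/7 × 147 = 126 and 6/7 × 161 = 138. The longest run is 6, so there is no relapse.

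**Fixed number of smoking days per week, placed at random.**
- Three days a week: a run can span at most two adjacent weeks, so it cannot exceed 3 + 3 = 6. P(relapse) = 0.
- Four days a week: each week has 35 equally likely patterns. Seven in a row needs at least 4 + 3 or 3 + 4 across a week boundary. P(last four days smoked) = 1/35, P(first three or more smoked) = 4/35 and P(exactly the last three smoked) = 3/35. Per boundary this is (1/35)(4/35) + (3/35)(1/35) = 7/1225 = 0.57%. Summing over 8 or 20 boundaries bounds the risk at 4.6% to Week 12 and 11.4% to Week 24. Exact enumeration gives 4.5% and 10.9%.
- Five and six days a week: by the same enumeration.

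| Smoking days per week | P(relapse) to Week 12 | P(relapse) to Week 24 | Scored never relapsed to Week 24 |
|---|---|---|---|
| 3 | 0% | 0% | 100% |
| 4 | 4.5% | 10.9% | 89% |
| 5 | 51% | 83% | 17% |
| 6 | about 100% | about 100% | about 0% |

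**Sensitivity to the pattern.** If each day is instead an independent draw with the same average, longer runs occur. P(relapse) to Week 24 is then 20% at 3/7, 73% at 4/7 and 99% at 5/7. The share escaping is 80%, 27% and 1%. The gap remains, but its size depends on how regular the smoking is.

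**Cotinine.** Take a participant at Week 12 who reports no smoking since quit day and has cotinine above 100 ng/ml. Abstinence (primary) scores a smoker. Prolonged abstinence has no seven-day run, so it scores abstinent. Continuous abstinence has no reported smoking, so it also scores abstinent. A participant who admits intermittent smoking gives no urine at all under footnote b.

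**Direction between arms.** As an illustration only, use the plan's Week 24 rates of 14.5% and 33.5% as stand-ins and let an assumed 10% of non-abstainers in both arms be misclassified. The rates become 0.145 + 0.10 × 0.855 = 23.1% and 0.335 + 0.10 × 0.665 = 40.2%. The difference falls from 19.0 to 17.1 points and the odds ratio from 2.97 to 2.24. Equal misclassification therefore dilutes the effect. An excess in the varenicline arm would work the other way, and the documents do not say which applies.

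**The case against.** The strongest reply is that intermittent smoking is already captured elsewhere. The primary outcome fails on any puff, continuous abstinence fails on any reported smoking, and lapses, recoveries and cigarette counts have their own analyses. The seven-day event is labelled openly, and the section attributes its measures to published recommendations, which cannot be examined here. This stands as a limit on the consequences. It does not close the gap, because prolonged abstinence is still analysed as a quit rate under a rule that admits current smokers.

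It can also be said that carbon monoxide and the urine dipstick are described as confirming smoking status in the same section. That wording could be read to cover prolonged abstinence, but nothing says so.

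Three stronger readings are tempting and are not supported:
- A reader might infer that anyone smoking six days a week counts as abstinent. That needs a smoke-free day at least every seventh day throughout. If the day moves at random, relapse by Week 12 is almost certain.
- A reader might infer that varenicline gains false abstainers, because Aim 1 expects reduction without full abstinence. That passage concerns daily cigarette counts. Someone who cuts down but still smokes daily relapses under the rule.
- A reader might put the inflation at so many percentage points by assuming a share of non-daily smokers. The documents give no such share, and the result would only restate the assumption.

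**Conclusion.** The point holds for prolonged abstinence, time to relapse and the lapse/relapse split, and, for the missing biochemical check, for continuous abstinence too. The primary outcome is not affected.

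At three to four smoking days a week, a participant is nearly always scored as never relapsed (89% to 100% to Week 24), given a constant weekly number of smoking days placed at random. With independent days the figure is 27% to 80%. At five to six days a week the score depends on spacing, and 126 of 147 days is the best-spaced extreme. All Week 24 figures assume the grace period ends at Week 3.

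The case of a participant who enrols as a non-daily smoker, changes nothing and is scored a success rests on the entry criterion of one cigarette a day on average. That conflicts with the five a day in Target Population, and the two must be reconciled. The gap does not depend on that case, because a daily smoker who becomes an intermittent one is scored in the same way.

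This is a faulty secondary-outcome rule that is worth a cheap correction. It is not a threat to the trial's main conclusion.

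**What to change.** In the Protocol Abstract and Other Smoking Measures (secondary):

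1. Add a second relapse criterion for recurrent intermittent smoking, for example smoking on at least 1 day in each of 2 consecutive weeks. Use it for time to relapse as well. State how weeks are counted and which day dates the event.
2. Redefine a lapse as smoking that meets neither relapse criterion. Otherwise one pattern would be both a lapse and a relapse. Carry this into the lapse and recovery models.
3. Count prolonged or continuous abstinence to Week 12, 18 or 24 only if the participant is also cotinine-verified abstinent at that visit under the Abstinence (primary) rule. This also brings in that rule's treatment of missing contacts and samples.
4. Keep the 7-consecutive-day self-report definition as a sensitivity analysis.
5. Reconcile the minimum smoking rate between Target Population and Key Inclusion Criteria.

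The two-week threshold is a suggestion and is not derived from the documents. The cost is wording and recoding of TLFB and cotinine data already collected, with no new visit or assay. The price is somewhat lower secondary abstinence rates and less direct comparability with the group's earlier trials, which item 4 preserves.
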